11.0 Study Withdrawal/Discontinuation***Diet Adherence Assessment***

Patients will be assessed for adherence to the controlled diet on Day 3 of the controlled diet outpatient period. Subject who do not meet a minimum 90% adherence will be withdrawn from the study. This will be determined by evaluating meal check lists and returned uneaten foods. During the 48-hour absorption testing as inpatients, subjects must show at least 90% adherence with the study diet and complete urine and fecal collections to be eligible to continue the additional 12-days (5 as inpatient) for full balance and kinetic measures. This is to ensure high quality balance data for these preliminary studies.

Participants may withdraw themselves from the study at any time by informing the study staff. The study staff may ask the participant if they are willing to talk about their reason for wanting to withdrawal from the study and if they are willing to discuss potential accommodations that might be possible that would make continuing the study possible, if appropriate. The study staff will explicitly let the participants know that they are not obligated to give a reason or discuss ways they might change their mind.

For participants who do not complete the entire study, data for the completed portions will be used for secondary/exploratory analyses, when statistically appropriate, unless the subject withdraws their consent for use of their data.

12.0 Statistical Considerations

This is a pilot study to determine effect sizes and variance estimates in fractional Ca, P, and Mg intestinal absorption (Aim 1) and Ca, P, and Mg balance (Aim 2) in patients with moderate CKD on a low Ca/High P (LCa/HP) diet vs. low Ca/low P (LCa/LP) diet. These data will be used for power calculations to determine an adequate sample size for a subsequent clinical trial to be proposed in an R01.

Four participants will be enrolled in this randomized cross-over study, 50% female, and we aim for at least ¼ black/African American and at least ¼ white race. All N = 4 will be included in Aim 1 with the primary outcomes of fractional Ca, P, and Mg absorption from a 48-hour testing periods. A subset of N = 2 subjects will be studied under Aim 2, with a week of Ca, P, and Mg balance and full kinetic model (12 days (5 as inpatient) beyond the initial 48-hour inpatient absorption test protocol).

At the beginning of the study, the study biostatistician ([name]) will generate a randomization list for dietary intervention crossover order A or B by pairs. These orders will be [LCa/HP to LCa/LP] or [LCa/LP to LCa/HP]. Especially due to the small sample size, attention will be made to ensuring a balance of the two orders, which will be accomplished by randomizing both in pairs.

Based on our experience, we anticipate only a 15% attrition rate, which is only 0-1 enrolled subjects needing to be replaced. However, because of the small sample size of 4 and the need for high adherence due to the preliminary nature of these studies, we seek approval enrolling up to 6 subjects to complete our planned n = 4.

Statistical Analysis: A repeated measures analysis of variance (ANOVA) for cross-over designs will be used to compare the LCa/HP diet with the LCa/LP diet on the primary outcomes:

Aim 1:	Aim 2:
Fractional Ca Absorption	Ca Balance
Fractional P Absorption	P Balance

Data will be examined for outliers and distributional model assumptions will be checked. Remedial measures will be taken as needed.

Power Calculations: The sample size required for the future R01 proposal will be based on the mean differences observed in the primary outcomes between the LCa/HP and LCa/LP diets, as well as the within- and among-patient variance estimates. We will determine sample sizes needed to detect a range of mean differences between diets with 80% to 90% power for a cross-over study.

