3.0 Outcome Measures/Endpoints

3.1 Primary Outcome Measures

1. **Fractional Ca Absorption**, by kinetic modeling of Ca-44 isotopic data (by ICP-MS) over 48 hour between Days 8-10
2. **Fractional P Absorption**, by kinetic modeling of P-33 isotopic data (from scintillation counting) over 48 hour between Days 8-10
3. **Calcium Balance**, calculated from diet, urine, and fecal Ca assessed by ICP-OES, throughout Days 8-14

4. **Phosphorus Balance**, calculated from diet, urine, and fecal P assessed by ICP-OES, throughout Days 8-21(the last week is outpatient follow-up)
5. **Calcium Kinetics**, by full kinetic modeling of Ca-44 isotopic data (by ICP-MS), throughout Days 8-21(the last week is outpatient follow-up)
6. **Phosphorus Kinetics** by full kinetic modeling of P-33 isotopic data (by scintillation counting), throughout Days 8-21

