6.0 Enrollment/Randomization

We aim to study N = 4 subjects, although seek approval enrolling up to 6 subjects due to the small sample size of 4 and the need for high adherence. Based on study diet and urine and fecal collection adherence of >90%, N = 2 patients that meet this level of adherence will be asked to continue with the full balance and kinetics protocol (Aim 2) on a first-enrolled basis. Thus 2 subjects will complete the absorption study (Aim 1), and 2 subjects will complete the full balance and kinetic studies (Aim 1 and Aim 2). It will be determined before a subject signs consent which consent they will sign (Consent A = Aim 1 or consent B= Aim 1 and Aim 2).

Recruitment will target moderate stage CKD patients aged 30-75 years old. Subjects will be recruited from patients seen in CKD clinics of the IU/Eskanazi Nephrology group who are partners of the co-investigators.

- Personnel from the IUSM Division of Nephrology will review medical charts from nephrology clinics for pre-screening to determine potential eligibility. An email will be sent to the doctors of the identified potential subjects to obtain their permission for enrollment and the potential subjects will be contacted by phone or visited by study staff during clinic.
- Information about the study may be discussed with interested potential subjects by research personnel by phone, email or in person as preferred by the subject/clinic.
- If interested, potential subjects will be either 1) scheduled for a screening visit at the Indiana Clinical Research Center, or 2) have screening information collected at the time of recruitment if subject is recruited in person at a CKD clinic by study staff.
- Prior to screening, subjects will be asked to provide written informed consent, and will be given the opportunity to have their questions about participation answered.
- Following the screening visit, all data will be evaluated by the study staff to determine eligibility of the subject. If eligible, participants will be enrolled in the study, and study visit dates will be scheduled.

Randomization Plan

At the beginning of the study, the study biostatistician will generate a randomization list for dietary intervention crossover order A or B by pairs. These orders will be A=LCa/HP to LCa/LP and B=LCa/LP to LCa/HP. Especially due to the small sample size, attention will be made to ensuring a balance of the two orders, which will be accomplished by randomizing both in pairs.

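### With two patients in Aim 2, the cross-over ANOVA for Ca and P balance has at most 1 residual df, so it cannot supply the balance variance meant to size the R01

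*Combined protocol and SAP*

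**What the plan says.** Section 12.0 of the combined protocol and SAP describes a pilot that is to yield effect sizes and variances for absorption (Aim 1) and balance (Aim 2). Sections 1.0 and 2.0 give the same purpose.

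- **Analysis.** "A repeated measures analysis of variance (ANOVA) for cross-over designs will be used to compare the LCa/HP diet with the LCa/LP diet" on four listed outcomes: fractional Ca and P absorption (Aim 1), and Ca and P balance (Aim 2). The model terms are not given, so it is not stated whether period is fitted.
- **Sample size.** "A subset of N = 2 subjects will be studied under Aim 2". Extra enrolment does not raise this number: "we seek approval enrolling up to 6 subjects to complete our planned n = 4".
- **Use of the result.** Under Power Calculations, the R01 sample size rests on the observed mean differences "as well as the within- and among-patient variance estimates". A range of mean differences will be examined at 80% to 90% power. No range of variances and no outside variance is mentioned.
- **Who enters Aim 2.** Orders are randomized in pairs. Under Section 6.0, adherent patients "will be asked to continue with the full balance and kinetics protocol (Aim 2) on a first-enrolled basis", and the consent version (Aim 1 only, or both aims) is settled before signing. Section 11.0 adds that "subjects must show at least 90% adherence with the study diet and complete urine and fecal collections to be eligible to continue". Nothing requires the two Aim 2 patients to have opposite orders.
- **Outcome.** Section 3.1 defines Ca balance as "calculated from diet, urine, and fecal Ca assessed by ICP-OES, throughout Days 8-14". I read this as one value per patient per diet.

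**The concern.** A pilot may be small and unpowered. This one, however, names variance estimates as its product and says what they are for. A 2 x 2 cross-over estimates the within-patient variance from the disagreement between patients' diet differences after allowing for period. Two patients give two differences, so almost nothing is left to estimate it from.

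At stake is the sample size of the later trial for Ca and P balance. The R01 would receive either no within-patient variance for these outcomes, or a 1-df figure that looks like an ordinary estimate and would go into a sample-size formula.

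**Working it through.** **Inputs.** Two patients, two periods, two diets (Sections 5.0 and 12.0); one balance value per patient per diet (reading of Section 3.1); R01 power of 80% to 90% (Section 12.0). The documents give no alpha, SD, effect size or precision target for N = 2, so that figure cannot be reproduced. The df count needs none of these.

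**1. Residual df.** There are 2 x 2 = 4 values per mineral. Residual df = values minus rank of the design matrix.

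| Orders of the two patients | Model | Rank | Residual df | Diet separable from period? |
|---|---|---|---|---|
| Opposite | patient + diet + period | 4 | 0 | Yes |
| Opposite | patient + diet | 3 | 1 | Only if there is no period effect |
| Same | patient + diet + period | 3 | 1 | No |

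For scale, Aim 1 (four patients, two per order) has 8 values: 8 - 6 = 2 df with period, 8 - 5 = 3 without.

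**2. The same result by hand.** Let d be a patient's LCa/HP minus LCa/LP difference, δ the diet effect, π the period effect (second minus first) and σ² the variance of d.

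- Opposite orders: d₁ has mean δ - π and d₂ has mean δ + π. These are two differences and two unknowns. The diet estimate is (d₁ + d₂)/2, the period estimate is (d₂ - d₁)/2, and nothing is left over.
- Opposite orders, period dropped: the variance estimate is (d₁ - d₂)²/2. Since d₁ - d₂ has mean -2π and variance 2σ², its expectation is σ² + 2π². Any period effect goes straight into the variance.
- Same order: both differences have the same mean, δ - π (or δ + π). There is 1 df for σ², but the data estimate only that combination, not δ.

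**3. Among-patient variance.** Two patients give one between-patient contrast, so at most 1 df. With opposite orders it is also the contrast between orders, and 0 df remain if a sequence effect is fitted.

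**4. Precision on 1 df** (normal data and, for opposite orders, no period effect). The 95% limits for the true variance are the estimate divided by the chi-square quantiles.

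- Lower: 1/5.024 = 0.20. Upper: 1/0.000982 = 1,018.
- As multiples of the SD: 0.45 to 31.9.
- One-sided 80% upper limit for the variance: 1/0.0642 = 15.6 times the estimate.
- Chance that the estimate is below half the true variance: P(chi-square on 1 df < 0.5) = 0.52.

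**5. Effect on the R01** (large-sample approximation, two-sided 5% assumed, mean difference held fixed). Required N is proportional to the variance. A variance at half its true value therefore gives half the needed N, and a smaller variance gives less.

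- 80% target: Φ((1.960 + 0.842) x √0.5 - 1.960) = Φ(0.021) = 0.51.
- 90% target: Φ((1.960 + 1.282) x √0.5 - 1.960) = Φ(0.332) = 0.63.

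These are upper bounds on true power in the 52% of cases where the estimate is below half the true value.

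**The case against.** The strongest reply is that this is openly a pilot producing preliminary data. No participant's safety is affected, and harm follows only if a later proposal uses the variance uncritically. Pilot status does excuse the lack of a power calculation, and Aim 2 keeps its descriptive and feasibility value. It does not excuse this gap, because variance estimation is the declared purpose and the stated basis for the R01.

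Other replies do not repair it:

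- The range of mean differences leaves the variance at its single observed value.
- The sentence on remedial steps concerns outliers and distributional assumptions. It cannot restore missing df.
- Enrolling up to six is meant to complete four. Aim 2 stays at two.
- Daily balances are not planned; Section 7.0 specifies 24-hour pools only for urine. For Ca over Days 8-14, 2 x 2 x 7 = 28 rows less rank 4 would leave 24 df, but all within patient-period cells. They measure day-to-day variation, and the cell-level residual in the opposite-order model with period stays at 0.

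A reader might infer that the two Aim 2 patients are likely to share an order. The documents do not support a probability. They randomize in pairs, settle the consent version before signing, and give no rate of qualifying for Aim 2. The shared order is only a case the plan does not rule out.

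**Conclusion.** The point stands for Ca and P balance. The planned ANOVA has 0 residual df with opposite orders and period fitted, and 1 df in the other cases set out above. The 0-or-1 count is exact for one value per patient per diet and depends on no assumed effect or SD. The limits of 0.20 to 1,018 also assume normality and, with opposite orders, no period effect. The power bounds of 51% and 63% also assume a fixed mean difference and a large-sample formula. Aim 2 therefore cannot supply the balance variance that the plan says will size the R01.

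Three stronger conclusions might be drawn and are not supported:

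- That no diet difference can be estimated. With opposite orders it can; its uncertainty cannot, once period is fitted.
- That the pilot gives the R01 nothing. Aim 1 has four patients and 2 to 3 df, which is weak but estimable, and is outside this point.
- That the df argument covers the kinetic outcomes. Section 12.0 does not list them under this ANOVA, so the point is confined to balance.

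This should be corrected before the analysis, because the stated output of Aim 2 is one that its design cannot deliver.

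**What to change.** **Section 12.0, Statistical Analysis.** Remove Ca and P balance from the ANOVA and add:

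> For Ca and P balance (N = 2), each participant's value on each diet, the LCa/HP minus LCa/LP difference and the diet order will be listed. Any SD shown is descriptive (at most 1 df) and will not be used alone to size the R01.

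**Section 12.0, Power Calculations.** Add:

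> R01 sample sizes for Ca and P balance will be shown over a range of SDs, informed by external data if suitable data are found.

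**Sections 1.0, 2.0 and 12.0.** Qualify the statements that Aim 2 yields balance variance estimates for sample size.

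The group's earlier balance study in CKD patients, cited in Section 7.0, is one possible external source. Its listed title concerns oral calcium carbonate, so its relevance to P restriction would have to be checked. The plan should not depend on it.

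**Cost.** Wording only, with no extra patients, samples or procedures. The stated output of Aim 2 becomes less favourable, and someone has to choose and justify the range of SDs for the R01.

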levels of Ca or P do not reflect whole-body status of either mineral (14, 15). This challenges both clinical research on Ca and P homeostasis, as well as clinical treatment decision-making. Thus, there is a **critical need** for knowledge of whole-body Ca and P physiology that can only be obtained from formal metabolic balance and kinetic studies of both ions simultaneously. However, such studies are largely absent in the scientific literature. Thus, **significant knowledge gaps** exist regarding whole-body Ca and P physiology that include how dietary Ca and P intakes, as well as kidney disease and its treatments, influence both Ca and P whole-body retention, intestinal absorption, and the transfer of Ca and P to and from the various body pools, such as intestine, bone, blood, and soft-tissue. Dietary P restriction is a commonly prescribed therapy for patients with CKD because it is presumed to reduce P retention and serum P, but this is based on little evidence (16). It is important to determine the effectiveness of dietary P restriction on its proposed benefits, because it is a difficult diet for patients to follow and may lead to consequences such as dietary protein or calcium deficiency, which can have negative consequences for bone health and mortality risk. The **goal** of this project is to generate preliminary data, including estimates of effect sizes and variances, on the effects of dietary P restriction therapy on Ca and P whole-body balance and full kinetics in patients with CKD. We will use this data in a future large research grant proposal that will include an adequately powered study to test the **hypothesis** that a high P diet, in the context of a typical low Ca diet, leads to P retention with negative Ca balance, and that dietary P restriction modestly reduces P retention but does not alleviate negative Ca balance. This will provide a foundation for further studies examining the effects of other factors on whole-body Ca and P physiology, including common pharmaceutical agents (e.g., various P binders, calcitriol, and calcimimetics), biological factors (e.g., age, race, and sex), CKD severity, and other nutritional interventions.

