2.0 Objectives

Aim 1. Determine intestinal Ca P, and Mg fractional absorption, effect sizes and variance estimates in patients with CKD on a low Ca diet with high P diet versus dietary P restriction. We will give CKD patients oral and IV Ca P and **and Mg** isotopes during a controlled-feeding, 48-hour inpatient study. In this study, we will use two dietary conditions and a randomized 2-period, cross-over design (low Ca/high P & low Ca/low P). Fractional Ca, P and Mg intestinal absorption will be determined by kinetic modeling of serum and urine oral and IV tracer data.

Aim 2. Determine Ca, P, and Mg balance and full kinetics, effect sizes and variance estimates in patients with CKD on a low Ca diet with high P diet versus dietary P restriction. A subset of subjects from Aim 1 will be studied as inpatients for an additional 12 days (5 as inpatient) after the 48-hour inpatient absorption testing protocol and in the same randomized 2-period cross-over design with the low Ca/high P & low Ca/low P diets. Total Ca, P, and Mg data will be determined from diet, urine, and fecal samples, and will be used to determine mineral balances. Further, we will use serum, fecal, and urine tracer data to determine full kinetic modeling including rates of transfer of the three ions between body pools, such as to and from bone.

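### The R01 sample size is to be based on this pilot's variance estimates, but two balance subjects cannot give a usable variance and four absorption subjects give a very imprecise one

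*Combined protocol and SAP*

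**What the plan says.** The Background (section 1.0) gives the purpose of the pilot: "We will use this data in a future large research grant proposal that will include an adequately powered study". The hypothesis for that later study is about balance, namely that "dietary P restriction modestly reduces P retention but does not alleviate negative Ca balance". Aim 2 in section 2.0 is accordingly to "Determine Ca, P, and Mg balance and full kinetics, effect sizes and variance estimates".

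Section 12.0 sets the numbers. Four subjects contribute to absorption (Aim 1), and for balance "A subset of N = 2 subjects will be studied under Aim 2". The comparison is a repeated measures ANOVA for cross-over designs. Whether it includes a period term is not stated.

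The Power Calculations paragraph in the same section bases the R01 sample size on the "mean differences observed in the primary outcomes between the LCa/HP and LCa/LP diets, as well as the within- and among-patient variance estimates". It then adds: "We will determine sample sizes needed to detect a range of mean differences between diets with 80% to 90% power". So the difference and the power are varied. The section mentions no confidence limit, range or external source for the variance.

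On who enters Aim 2, section 6.0 says that subjects who reach the adherence level "will be asked to continue with the full balance and kinetics protocol (Aim 2) on a first-enrolled basis". The two orders are randomised in pairs.

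**The concern.** The main product of this pilot is a set of planning values. A planning variance is only as good as its residual df, and here they are at or near zero for the outcomes that the later hypothesis concerns. If the Power Calculations paragraph is followed as written, the balance sample size would rest on a variance that either does not exist or is almost undetermined. The absorption sample size would rest on one that can easily be several times too small. An R01 trial sized that way could be well short of its nominal power, and the proposal would give no sign of it.

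**Working it through.** The documents give no SD, effect size or computed sample size on this point, so there is no figure of the plan's own to reproduce.

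**Inputs.** N = 4 for absorption, N = 2 for balance, two periods per subject, and power of 80% to 90% (all from section 12.0; the two-period design also from section 5.0). Assumed here and not stated in the documents: two-sided 5% significance and normally distributed data.

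**Step 1: residual df.** These equal the number of observations minus the rank of the model with subject, diet and, optionally, period.

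| Outcome | Orders | With period | Without period |
|---|---|---|---|
| Balance, N = 2 | opposite | 4 − 4 = 0 | 4 − 3 = 1 |
| Balance, N = 2 | same | 4 − 3 = 1 | 4 − 3 = 1 |
| Absorption, N = 4 | two of each | 8 − 6 = 2 | 8 − 5 = 3 |

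In the same-order row the period column is identical to the diet column up to sign and a constant. Diet and period therefore cannot be separated, and no interpretable diet effect is available.

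**Step 2: precision of the within-patient SD.** With df·s²/σ² distributed as chi-square on df degrees of freedom, the 95% limits for σ are s·√(df/χ²₀.₉₇₅) and s·√(df/χ²₀.₀₂₅).

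- 1 df: √(1/5.024) = 0.45 to √(1/0.000982) = 31.9 times s.
- 2 df: √(2/7.378) = 0.52 to √(2/0.0506) = 6.3 times s.
- 3 df: √(3/9.348) = 0.57 to √(3/0.2158) = 3.7 times s.

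At 0 df there is no estimate at all.

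**Step 3: what planning at the estimate does to absorption.** For a 2×2 cross-over with N subjects in total, N = 2σ²(1.96 + 0.84)²/δ², and (1.96 + 0.84)² = 7.85 using unrounded normal quantiles. If s² replaces σ² and δ is held at its true value, the power actually obtained is Φ(√(7.85u) − 1.96), where u = s²/σ² follows chi-square(df)/df. Averaged over u:

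- nominal 80%: 0.605 at 2 df, 0.652 at 3 df;
- nominal 90% (10.51 in place of 7.85): 0.675 at 2 df, 0.730 at 3 df.

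These averages do not depend on an assumed effect size, because δ cancels.

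**Step 4: does the range of differences cover it?** The one-sided 80% upper limit for the variance is df/χ²₀.₂₀ times the estimate: 2/0.4463 = 4.48 at 2 df and 3/1.0052 = 2.98 at 3 df. Since N depends on σ²/δ², a variance 4.48 times as large needs the same N as a difference 1/√4.48 = 0.47 times as large. A range of differences reaching down to about half the planning value would thus have a similar effect at 2 df. The plan does not say how wide its range will be or link it to the variance.

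**Step 5: size of the change in displayed N.** At 80% power, N is about 2 × 7.85/d², where d is the planning difference in estimated SDs (illustrative values).

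| d | at the estimate | at 4.48 × (2 df) | at 2.98 × (3 df) |
|---|---|---|---|
| 0.5 | 63 | 281 | 187 |
| 0.75 | 28 | 125 | 83 |
| 1.0 | 16 | 70 | 47 |

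Values are rounded to the nearest whole number.

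**The case against.** The study calls itself a pilot, says openly that N is 4 and 2, and already promises sample sizes over a range of differences. To base a sample size on pilot data is not to base it on them alone, and the team cites a previous balance study of its own in CKD patients. The R01 will have its own protocol and review. All of this is fair. It means that the number of subjects is not at fault and that nothing in this pilot's conduct is in question. It does not supply a balance variance. Section 12.0 names no other source, section 7.0 cites the earlier study only in connection with the vitamin D supplement, and the documents do not show whether that study yields a usable within-patient variance.

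Three stronger readings are tempting and should not be adopted.

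- A reader might infer that a sample size planned at the estimate will more often than not be too small. As a count of shortfalls this is a weak measure, because the chi-square distribution is skewed and the chance that s² lies below σ² exceeds one half at any df: 63% at 2 df, but still 54% at 20 and 52% at 100. With whole-number N it also depends on an effect size that the documents do not give. The loss of mean power in Step 3 is the better measure.
- A reader might infer that the two Aim 2 subjects are likely to share an order. Pairing makes the first two enrolled take opposite orders unless one drops out or fails on adherence. Section 6.0 also has the choice of consent made before signing. The documents do not describe replacement well enough to put a probability on it. Same-order selection is possible, and no more than that can be said.
- A reader might infer that observed differences should be barred from planning. That is a preference, and effect sizes are a stated product of the pilot. Reporting them with their uncertainty is enough.

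**Conclusion.** The concern holds for the variance. For balance, the stated rule cannot produce a usable planning value: 0 df with a period term, or 1 df and an SD known only to within 0.45 to 32 times its estimate. This conclusion follows from the design alone (normality is needed only for the interval). For absorption, a variance can be estimated, but on 2 or 3 df. Using it without allowance costs about 20 or 15 points of mean power at a nominal 80% (80 − 60 and 80 − 65), given normal data, a two-sided 5% test, a normal approximation and a fixed true difference. The range of differences in section 12.0 reduces the gap but does not close it.

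The change should be made, because this paragraph governs the pilot's main deliverable. It does not affect participants or the validity of the pilot itself.

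**What to change.** Amend the Power Calculations paragraph in section 12.0 along these lines:

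> The N = 2 balance results will be descriptive and will not be the sole source of the planning variance for the R01. An external within-patient variance will be used if one can be obtained; otherwise an assumed range will be stated. For fractional absorption, sample sizes will be shown over the planned range of between-diet differences, at 80% and 90% power, using both the estimated within-patient variance and an upper confidence limit for it (for example one-sided 80%), as a sensitivity range. Observed differences will be reported with 95% confidence intervals where estimable.

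The multiplier for the upper limit is 4.48 if the ANOVA has a period term and 2.98 if it does not, so it should be taken from the model actually fitted.

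The cost is a wider and less favourable set of sample sizes in the R01 proposal, as the last table in the working shows. The upper limit is for display and is not a mandated N. If it were adopted as the final N, the median would be about 3.1 times the correct one at 2 df and 2.35 times at 3 df. That trade-off is for the team to judge. Enrolment, procedures and follow-up in this pilot are unchanged.
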